COMIRB Protocol

COLORADO MULTIPLE INSTITUTIONAL REVIEW BOARD
[name] [contact] [contact]

Protocol #: 18-0369
Project Title: Effects of Exercise on Sleep Quality and Nocturnal Fat Oxidation in Individuals with Metabolic Syndrome
Principal Investigator: [name]
Coinvestigator: [name]
Version Date: 8/24/20

I. Hypotheses and Specific Aims:

Our long-term goal is to understand how physical activity and sleep interact to influence cardiovascular disease and diabetes risk, and use these findings to tailor interventions for individuals prone to sleep disorders (e.g., individuals with metabolic syndrome, older adults). This pilot study will generate key preliminary data to inform an in-depth mechanistic study to investigate factors that may modulate the relationship between exercise and sleep and their subsequent metabolic impact (e.g. dietary fat oxidation, insulin sensitivity). Specifically, **to determine the effects of daytime exercise on sleep quality and nocturnal metabolism, and to explore potential mechanisms by which exercise-induced changes in nocturnal metabolism and sleep quality occur. The specific aims are:**

Aim 1: Determine the effects of daytime exercise on nocturnal metabolism and sleep quality. The primary outcome is nocturnal FFA concentrations. Secondary outcomes are nocturnal fat oxidation, nocturnal glucose and insulin concentrations, and sleep quality (e.g. percent time in slow wave sleep [SWS], sleep latency, and wake after sleep onset [WASO]). To capture the dynamic changes in nocturnal hormones and metabolites, I will perform overnight hourly blood sampling. Fat oxidation will be measured using whole-room indirect calorimetry. Sleep quality will be assessed using gold standard polysomnography. I hypothesize that exercise will increase nocturnal FFA concentrations and fat oxidation, and reduce nocturnal glucose and insulin concentrations. I further hypothesize that exercise will increase percent time in SWS and decrease sleep latency and WASO.

Aim 2: Determine whether exercise-induced changes in nocturnal fat and glucose metabolism and sleep quality are associated with the known improvements in next day insulin sensitivity. Insulin sensitivity will be measured by intravenous glucose tolerance test in the morning upon waking. I hypothesize exercise-induced changes in nocturnal metabolism and sleep quality will be associated with improved next day insulin sensitivity.

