Exploratory Aim: Explore mechanisms that contribute to exercise-induced changes in nocturnal fat and glucose metabolism and sleep quality. Outcomes are distal-proximal skin temperature gradients and melatonin offset. Data generated from this exploratory aim will provide preliminary data to power a more mechanistically-driven studies of the impact of daytime exercise on sleep quality and nocturnal metabolism.

II. Background and Significance

1.1 Exercise and metabolic syndrome (MetS) risk: Exercise reduces the risk of acquiring the MetS (a clustering of several metabolic disorders) and is the cornerstone of behavioral lifestyle interventions (23). The presence of MetS, increases the risk of cardiovascular disease and diabetes more than when any of these disorders is presented alone (2, 30). While the health benefits effects of exercise are well documented (e.g. improved insulin sensitivity and increased post-exercise fat oxidation), the impact of exercise on metabolism during sleep, a time frame that occupies approximately a third of the human lifespan, are largely unknown.

1.2 Sleep quality, nocturnal fat metabolism and risk of MetS: A strong body of evidence has accumulated indicating that impaired sleep contributes to the development of components of the MetS (20, 29, 34, 38, 39). Interestingly, the nocturnal period is full of dynamic changes in many hormones (e.g. insulin, growth hormone) and metabolites (free fatty acids, glucose) (10, 11, 14). Several studies have shown that daytime behaviors (e.g. overfeeding) or disruptions in normal sleep patterns cause changes in nocturnal metabolism which, in turn, impact metabolic outcomes such as insulin sensitivity. Studies by my mentors have shown that experimental sleep restriction in humans causes increases in nocturnal free fatty acid (FFA) concentrations and impairments in insulin sensitivity (10). Additional studies by my mentor, [name], have shown that elevated nocturnal FFA concentrations may be an early signal that induces compensatory hyperinsulinemia in response to insulin resistance induced by a high

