Both of my co-mentors, [name] and [name], have implemented frequent nocturnal blood sampling in their inpatient studies to measure hormones and metabolites during sleep in humans (11). Specifically, [name] has preliminary data demonstrating that exercise performed in the morning and evening results in lower nocturnal insulin concentrations, increased FFA concentrations and increased fat oxidation (Figure 1, unpublished data). At night, concentrations of the antilipolytic hormone insulin are low (8) while concentrations of hormones promoting lipolysis (e.g. growth hormone, and glucagon) are high (33, 40, 41). This nocturnal hormonal milieu results in increased FFA availability and increased fat oxidation (3, 24, 32). It seems plausible that exercise potentiates this latter effect. These preliminary data from [name] demonstrate that exercise can influence the nocturnal metabolic environment. However, because energy expended during exercise was not replaced in the diet, it is unclear from this study whether the observed effects are due to exercise or energy deficit. Further, the mechanisms driving alterations to nocturnal FFA and fat oxidation in response to exercise are not known and deserve investigation.

IV. Research Methods

A. Outcome Measure(s):

The primary outcome is nocturnal FFA concentrations. Secondary outcomes are nocturnal fat oxidation, nocturnal glucose and insulin concentrations, and sleep quality (e.g. percent time in slow wave sleep [SWS], sleep latency, and wake after sleep onset [WASO]). An exploratory outcome is the distal-proximal skin temperature gradient (DPG). The methods that will be used to measure these outcomes are described below in section C (Study Design and Research Methods).

[figure not shown]
B. Description of Population to be Enrolled:

Physically inactive men and women (N=18, [9 men, 9 women]; 19-45 years) will be recruited from the local Denver area. Individuals must have overweight or obesity and central adiposity as defined by waist circumference >40 inches (men) or >35 inches (women). Additional inclusion and exclusion criteria are:

- **Inclusion criteria:** not currently meeting physical activity guidelines (<150 minutes moderate to vigorous physical activity per week); weight stable (<5% change in weight over the last 6 months); habitual sleep duration of 7-8 hours and consistent sleep/wake schedule (<1 hour variation night-to-night).

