- **Exclusion criteria:** body mass index (BMI) $\geq 35.0 \text{ kg/m}^2$; pregnancy; post-menopausal status in women, confirmed by elevated follicular stimulating hormone concentrations ($>50 \text{ mIU/mL}$); hormonal contraception in premenopausal women; self-reported diabetes, cardiovascular disease, untreated hyper/hypothyroidism, or cancer; inability to perform moderate to vigorous treadmill exercise; a clinical diagnosis of a sleep disorder (e.g. sleep apnea); working night shifts or traveling across more than 2 time zones within 1 month of and throughout the study; currently taking medications for glucose management, thyroid conditions or blood pressure control. Anyone who has experienced a serious illness within the last 6 months (per discretion of PI and study MD). Anyone with a confirmed positive COVID test within the last 6 months (per discretion of PI and study MD)

C. Study Design and Research Methods

D. 3.1 Overview of Study Design (Figure 2): Participants will perform 4 study visits over 2-3 months. Eligibility will be determined during the 1st visit (screening visit). During the 2nd visit, resting metabolic rate (RMR) and body composition will be measured. Habitual sleep/wake patterns will then be measured for 1 week. Participants will then perform each of the 3 study conditions (visits 3-4) in randomized order with at least a 1-week washout period between conditions.

Visit 1, Screening Procedures: After preliminary telephone screening, participants will attend a virtual screening visit to determine eligibility. Participants will provide written informed consent (via RedCap or by sending a scanned copy of the signed informed consent to the study coordinator email). Participants will then complete a medical history questionnaire and a sleep quality questionnaire (Pittsburgh Sleep Quality Index, PSQI (12)). All questionnaires will be completed on RedCap.

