and to refrain from using electronic devices. Participants will be woken up the following morning at their habitual wake time. For subsequent in-patient study conditions, the timing of events during the study (e.g. CTRC arrival, bedtime) will be identical. During the EX condition, participants will perform 45-minutes of moderate intensity continuous exercise on a motorized treadmill 12 hours their habitual wake time in the evening (Figure 3). Prior to the exercise bout, participants will warm-up by walking on the treadmill for 5 minutes at 2.0-2.5 mph. Participants will wear a Zephyr heart rate monitor (Medtronic) to continuously track and record heart rate on a minute-by-minute basis using Bluetooth technology. Research staff will confirm start and stop time of exercise bouts to ensure participant compliance to the exercise bout. Participants will replicate the exercise bout performed during the submaximal exercise test during the baseline assessment (described in section D) and maintain heart rate at 65% of age-predicted maximum heart rate.

Energy intake will be standardized during each condition and will be provided as 3 discrete meals increasing in size over the day (breakfast: 25%, lunch: 35%, dinner: 40%) to simulate usual eating patterns of western adults (55). To compensate for anticipated lower physical activity levels while in the whole room calorimeter, energy intake (kcal/d) energy intake will be adjusted by multiplying RMR by an activity factor of 1.4. To ensure energy balance is maintained during the EX conditions, we will add back the calories expended during exercise evenly across breakfast, lunch and dinner (i.e. 300 kcal expended during exercise, 100 kcal will be added to each meal). We will use the measured EE during the baseline submaximal exercise test as an estimate of energy expended during exercise in the whole room calorimeter. To measure dietary fat trafficking, we will administer a D31 palmitate stable isotope tracer orally during the breakfast meal. Urine samples will be collected throughout the calorimeter stay to measure assess dietary fat oxidation.

Upon waking, participants will be given light blocking glasses to wear for the measurement of melatonin. Saliva samples will be collected hourly for 6 hours after waking to assess melatonin offset. Simultaneously, an intravenous glucose tolerance test (IVGTT) will be performed to assess insulin sensitivity.

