Statistical Analysis Plan: All statistical analyses will be performed using the R statistics and computing package. We will employ conventional approaches to the interpretation and reporting of results from statistical analyses (i.e. 2-sided p-values and 95% confidence intervals, and significance levels of 0.05 for all hypotheses tests). To accomplish **aim 1 and 2**, we will compare the effect of EX vs. CON our primary and secondary outcomes (described in section 3.1) using repeated measures linear mixed models with planned contrasts. To accomplish the **exploratory aim**, we will compare the effect of EX and CON on the distal/proximal gradient and melatonin responses and explore whether those differences are associated with changes in sleep quality and nocturnal metabolism. Finally, we will explore whether there are differences in any of our outcomes by sex.

G. Summarize Knowledge to be Gained:

Metabolic syndrome is a major risk factor for many chronic diseases, including diabetes and cardiovascular disease. Poor sleep quality is related to numerous poor health outcomes and is common among individuals with metabolic syndrome. Impairments in nocturnal fat metabolism are associated with insulin resistance and a strong predictor of subsequent weight gain. Exercise is a potential therapeutic target which may improve both sleep quality and nocturnal fat metabolism. Findings from the proposed study will identify how exercise influences novel contributors to metabolic syndrome (sleep quality and nocturnal metabolism) and elucidate potential mechanisms to explain the variability in exercise responses.

H. References:

2. Aschner P. Metabolic syndrome as a risk factor for diabetes. *Expert Rev Cardiovasc Ther*. 2010;8(3):407-12.
5. Bergman RN. Lilly lecture 1989. Toward physiological understanding of glucose tolerance. Minimal-model approach. *Diabetes*. 1989;38(12):1512-27.

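### Aim 2 asks about an association with next-day insulin sensitivity, but its only planned analysis is a comparison of EX and CON means

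*Combined protocol and SAP*

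**What the plan says.** Section I states Aim 2 as: "Determine whether exercise-induced changes in nocturnal fat and glucose metabolism and sleep quality are associated with the known improvements in next day insulin sensitivity". The hypothesis follows: "I hypothesize exercise-induced changes in nocturnal metabolism and sleep quality will be associated with improved next day insulin sensitivity". Both are about a relation between changes.

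The Statistical Analysis Plan in IV.F covers Aims 1 and 2 in one sentence: "we will compare the effect of EX vs. CON our primary and secondary outcomes (described in section 3.1) using repeated measures linear mixed models". That sentence also provides for planned contrasts. It names no correlation, regression of change on change, predictor term or mediation step for Aim 2.

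The next sentence, for the exploratory aim, does contain an association step: the investigator will "explore whether those differences are associated with changes in sleep quality and nocturnal metabolism". The differences meant are those in skin temperature gradient and melatonin, in line with that aim's definition in section I: "Outcomes are distal-proximal skin temperature gradients and melatonin offset". Insulin sensitivity plays no part in it.

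Section IV.A names nocturnal FFA as primary and continues: "Secondary outcomes are nocturnal fat oxidation, nocturnal glucose and insulin concentrations, and sleep quality". Insulin sensitivity is in neither tier there or in section I. It is nevertheless a planned measurement: the inpatient text says "an intravenous glucose tolerance test (IVGTT) will be performed to assess insulin sensitivity", and IV.D defines it as the minimal-model estimate. The cross-reference to section 3.1 leads to design text that opens "3.1 Overview of Study Design (Figure 2): Participants will perform 4 study visits over 2-3 months" and has no visible list of outcomes by tier. Figure 2 is not available in the text, so its content is not judged.

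**The concern.** An EX-versus-CON contrast estimates the average shift in one outcome. Aim 2 takes the average improvement in insulin sensitivity as already known. Its open question is whether that improvement follows the nocturnal and sleep changes from person to person, and that depends on the covariance of the changes, which separate mean contrasts do not estimate.

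The pilot is meant to supply preliminary data on how exercise and sleep interact and on the metabolic consequences, with insulin sensitivity given as an example (sections I and IV.F). Followed exactly, the plan would give no estimate of that link. There are then two risks. Parallel mean shifts in FFA, sleep and insulin sensitivity could be presented as support for Aim 2. Or the association model and its predictors could be chosen after the data are seen, with every test at 0.05.

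**Working it through.** **1. Inputs.** From IV.F: two-sided tests at 0.05; 18 recruited, 15% attrition, at least 15 completers. The recruitment figure reproduces: 15 / (1 - 0.15) = 17.6, rounded up to 18; and 18 x 0.85 = 15.3. IV.F speaks of completing three conditions while the inpatient text describes two (EX and CON). The calculation needs only one EX-CON pair per person, so that conflict does not affect it. The documents give no effect size, SD or correlation, so those below are assumptions shown over a range.

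**2. Does the planned contrast carry information on Aim 2?** Simulation of 20,000 trials with 15 pairs of changes, both outcomes shifted by an assumed 0.8 SD of the within-person change:

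| True correlation of changes | Power of each EX-CON test | Rejection by a test of association |
|---|---|---|
| 0 | 82% | 5% |
| 0.5 | 82% | 50% |
| 0.8 | 82% | 97% |

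The contrasts behave the same whether the association is absent or strong.

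**3. Precision of the missing analysis** (one correlation of changes, unadjusted).
- Smallest significant |r| = t / sqrt(n - 2 + t²). For n = 15, t(13) = 2.160: 2.160 / sqrt(13 + 4.667) = 0.514. For n = 18, t(16) = 2.120: 2.120 / sqrt(16 + 4.494) = 0.468.
- 95% CI for an observed r of 0.5: tanh(atanh(0.5) ± 1.96 / sqrt(n - 3)), with atanh(0.5) = 0.549. For n = 15: tanh(0.549 ± 0.566) = -0.02 to 0.81. For n = 18: tanh(0.549 ± 0.506) = 0.04 to 0.78.
- Power by simulation (bivariate normal changes, 200,000 trials per setting):

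| | n = 15 | n = 18 |
|---|---|---|
| Power at r = 0.5 | 50% | 59% |
| r for 80% power | about 0.65 | about 0.61 |
| r for 80% power, order-adjusted | about 0.67 | about 0.62 |

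The Fisher-z approximation gives slightly lower power without order adjustment: 48% at r = 0.5 for n = 15, with r of about 0.67 needed for 80%.

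**4. A caution for the replacement model.** With two conditions, a within-person model that omits the condition term is a regression of change on change through the origin. If both changes have mean d (in SD units) and are uncorrelated, its slope tends to d² / (1 + d²), which is not zero: 0.25 / 1.25 = 0.20 at d = 0.5, and 1 / 2 = 0.50 at d = 1. With n = 15 and no true association, it declares one in 11%, 33% and 56% of simulated trials for assumed shifts of 0.5, 0.8 and 1.0 SD. With the intercept (the condition term) the rate is 5%.

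**5. Multiplicity.** The primary outcome and the named secondary outcomes give seven candidate predictors. If none is truly associated, the chance of at least one p < 0.05 is 1 - 0.95^7 = 0.30 with independent predictors. In simulation it is 0.24 or 0.19 if they correlate at an assumed 0.5 or 0.7.

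**The case against.** The best defence is that IV.F names Aim 2 and a mixed-model framework, that such a model can hold a within-person predictor, and that a short pilot plan need not write out every model. This is weak. The sentence specifies only the condition effect, and the sentence after it shows that an association step is written down where one is intended.

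Other points on that side do stand, and they limit the concern:
- The IVGTT, nocturnal AUCs, calorimetry and polysomnography are all obtained in the same people under both conditions. The association remains computable, so what is lost is its prespecification, not the data.
- The power figures describe the missing analysis, and the condition-term figures describe a model the plan never proposes. They guide the remedy and do not measure the defect.
- The list of seven predictors is one reading. Sleep quality is introduced with examples, and IV.D adds the number of awakenings and several hormones. The investigator may prefer a shorter list.
- The section 3.1 pointer is a clerical slip, since IV.A lists the outcomes. Aim 2 itself names insulin sensitivity and its test, so the missing outcome label is minor.

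**Conclusion.** The concern holds. Aim 2 is a numbered aim with its own hypothesis, and the method assigned to it cannot answer it. Read literally, the sentence does not cover even an EX-versus-CON comparison of insulin sensitivity, because that measure is in neither outcome list.

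This should be fixed, but it does not threaten the trial's main result: the EX-CON test of nocturnal FFA is untouched, and the pilot makes no power claim. The mismatch rests on the text alone and needs no numerical assumption. The precision figures assume bivariate normal changes and one EX-CON pair per person. They show that 15 to 18 completers can detect only strong associations, with correlations of roughly 0.6 or more. That is a reason to plan Aim 2 as estimation, not to leave its analysis unwritten.

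**What to change.** In IV.F, separate Aim 2 from Aim 1 and make these changes:

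1. List IVGTT minimal-model insulin sensitivity as the Aim 2 outcome in sections I and IV.A, and point the outcome cross-reference to IV.A.
2. Regress each participant's EX-minus-CON change in insulin sensitivity, with an intercept, on the EX-minus-CON change in each of nocturnal FFA AUC, fat oxidation, glucose AUC, insulin AUC, percent SWS, sleep latency and WASO, or on a shorter list fixed in advance. An equivalent is a mixed model with a condition term, the within-person-centred predictor and the person mean. In five simulated two-condition datasets it gave the same within-person slope to four decimals.
3. Report slopes with 95% confidence intervals, state the expected precision, and say that EX-CON mean shifts will not be offered as evidence for Aim 2.
4. Decide and record three matters: whether to adjust for condition order; how the estrogen and progesterone covariates promised in IV.E enter this analysis, including whether they apply to men; and whether the associations are corrected for multiplicity or labelled as estimation.

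Relabelling Aim 2 as hypothesis-generating, with a short predictor list, would also suit a pilot, provided the association model is still written down.

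The cost is plan wording and a few regressions on data already to be collected. Visits, sampling and the primary test do not change. The drawback is that the plan will openly show how imprecise Aim 2 is with about 15 completers.
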